14.1.2 Primary Objective: Sensitivity Analyses of the primary endpoints

The robustness of the results of the primary analysis will be evaluated by the following

- Multiple Imputation to handle missing data using different assumptions,
- Non-parametric factorial model for longitudinal data,
- Generalized model assuming negative binomial distribution,
- Mixed-effects linear model with pooled-centers as fixed effects.

To evaluate further the impact of the potential zero inflation, the primary endpoint will be classified in different response categories for each Period as follows:

- Presence of MRI activity
 - Yes (CUA lesion count > 0)
 - No (CUA lesion count = 0)
- Standardized CUA lesion count classified to:
 - 0 (standardized CUA lesion count = 0)
 - >0 – 1 (standardized CUA lesion count > 0 and less or equal to 1)
 - >1 (standardized CUA lesion count > 1)

Analysis (Analysis Set)	Derivation	Statistical Analysis Methods	Missing data handling
Primary endpoints: Differences in the counts of CUA MRI lesions during the first 6 months (i.e., during Periods months 1-6, 2-6, 3-6) compared to Baseline Period (i.e., the Period from Screening to Baseline) (a).			
Sensitivity (FAS by subgroup "High-relapse activity")	Period 3 (Month 3-6): $\Delta\text{CUA}(p_3)$	Same as in the Primary Analysis (see Section 14.1.1)	Same as in the Primary Analysis (see Section 14.1.1)
	Period 2 (Month 2-6): $\Delta\text{CUA}(p_2)$		
	Period 1 (Month 1-6): $\Delta\text{CUA}(p_1)$		
Sensitivity (FAS by subgroup "Previous treatment with DMDs")	Period 3 (Month 3-6): $\Delta\text{CUA}(p_3)$		
	Period 2 (Month 2-6): $\Delta\text{CUA}(p_2)$		
	Period 1 (Month 1-6): $\Delta\text{CUA}(p_1)$		
Sensitivity (FAS for subset "Baseline Period CUA count > 0")	Period 3 (Month 3-6): $\Delta\text{CUA}(p_3)$		
	Period 2 (Month 2-6): $\Delta\text{CUA}(p_2)$		
	Period 1 (Month 1-6): $\Delta\text{CUA}(p_1)$		
Sensitivity (FAS)	Period 3 (Month 3-6): $\Delta\text{CUA}(p_3)$	Same as in the Primary Analysis (see Section 14.1.1)	Multiple Imputation (see below for details)
	Period 2 (Month 2-6): $\Delta\text{CUA}(p_2)$		
	Period 1 (Month 1-6): $\Delta\text{CUA}(p_1)$		
Sensitivity (FAS)	Period 3 (Month 3-6): $\Delta\text{CUA}(p_3)$	Non-parametric factorial model for longitudinal data. Fixed factors: 
 • Age in years ($\leq 40, 40 < 65$), • EDSS at Baseline ($\leq 3, > 3$), (see below for details)	Same as in the Primary Analysis (see Section 14.1.1).
	Period 2 (Month 2-6): $\Delta\text{CUA}(p_2)$		
	Period 1 (Month 1-6): $\Delta\text{CUA}(p_1)$		
Sensitivity (FAS)	Period 3 (Month 3-6): $\#\text{CUA}(p_3)/\#\text{CUA}(p_0)$	Generalized model assuming a negative binomial distribution with the following adjusting factors: 
 • Period • Age (in years), • EDSS at Baseline ($\leq 3, > 3$), • Within-pooled center correlations. Estimated standardized CUA for the Periods as well as the ratios of each post-Baseline Period versus the Baseline Period, and corresponding Standard Errors (SE) will be presented including estimated fixed effects including the SE, 2-sided p-values and 95% CI	Same as in the Primary Analysis (see Section 14.1.1).
	Period 2 (Month 2-6): $\#\text{CUA}(p_2)/\#\text{CUA}(p_0)$		
	Period 1 (Month 1-6): $\#\text{CUA}(p_1)/\#\text{CUA}(p_0)$		

Analysis (Analysis Set)	Derivation	Statistical Analysis Methods	Missing data handling
Sensitivity (FAS)	Period 3 (Month 3-6): $\Delta\text{CUA}(p_3)$ Period 2 (Month 2-6): $\Delta\text{CUA}(p_2)$ Period 1 (Month 1-6): $\Delta\text{CUA}(p_1)$	Mixed-effects linear model with the following adjusting factors: 
 • Baseline score, • Age (years), • EDSS at Baseline (≤ 3, >3), • Period, • pooled center. Estimated Least Square Means (LS Means) and corresponding Standard Errors (SE) will be presented by Visit including 2-sided p-values and 95% CI.	Same as in the Primary Analysis (see Section 14.1.1).
Categorization of the Primary Endpoints: Presence of MRI activity (at least one CUA lesion) during the first 6 months (i.e., during Periods 1-3 compared to Baseline Period (i.e., the Period from Screening to Baseline))^(a).			
Sensitivity (FAS)	Cross-tabulation for each Period i , where $i=1,2,3$ 
 • No: $\#\text{CUA}(p_i) = 0$ • Yes: $\#\text{CUA}(p_i) > 0$ vs Baseline Period: 
 • No: $\#\text{CUA}(p_0) = 0$ • Yes: $\#\text{CUA}(p_0) > 0$ 	McNemar Test.	Same as in the Primary Analysis (see Section 14.1.1).
Sensitivity (FAS by subgroup High-relapse activity)			
Sensitivity (FAS by subgroup "Previous treatment with DMDs")			

Analysis (Analysis Set)	Derivation	Statistical Analysis Methods	Missing data handling
Categorization of the Primary Endpoints: Classified CUA lesion count during the first 6 months (i.e., during Periods 1-3) compared to Baseline Period (i.e., the Period from Screening to Baseline)^(a).			
Sensitivity (FAS)	Cross-tabulation for each Period i , where $i=1,2,3$ 
 • 0: $\#CUA(p_i) = 0$ • $>0-1$: $0 < \#CUA(p_i) \leq 1$ • >1: $\#CUA(p_i) > 1$ vs Baseline Period: 
 • 0: $\#CUA(p_0) = 0$ • $>0-1$: $0 < \#CUA(p_0) \leq 1$ • >1: $\#CUA(p_0) > 1$ 	Bowker's test of symmetry.	Same as in the Primary Analysis (see Section 14.1.1).
Sensitivity (FAS by subgroup "High-relapse activity")			
Sensitivity (FAS by subgroup "Previous treatment with DMDs")			
$\Delta CUA(p_i)$ = Difference in the standardized CUA lesion count between Period i and the Baseline Period, $i=1$ (Month 1-6), 2 (Month 2-6), 3 (Month 3-6) $\#CUA(p_i)$ = Standardized CUA lesion count during Period i , $i=0$ (Baseline Period), 1 (Month 1-6), 2 (Month 2-6), 3 (Month 3-6) (a) 6-month interim analysis			

Multiple imputation

In order to evaluate the robustness of the assumption applied in the primary analysis that missing data are observed as missing at random (MAR), the primary analysis will be repeated applying a pattern mixture model. If missingness can be considered MAR (e.g. MRI missing for technical reasons), data will be imputed by multiple imputation from post-Baseline data while if it is considered as missing not at random (MNAR) (e.g. drop-out due to lack of efficacy), data will be imputed from Baseline data.

The multiple imputation procedure will use a pre-specified seed number repeating the imputation procedure 100 times.

The following reasons for missing MRI results will be considered as MAR:

- MRI classified as non-evaluable by the central MRI reading
- MRI missing at Baseline
- Subject discontinued the study before the Month 6 Visit with primary reason
 - Lost to follow-up
 - Any Protocol non-compliance reported as “Other” and classified as non-related to study treatment
 - Any withdrawal of consent classified as non-related to study treatment
 - Any pregnancy (Discontinuation Reason “Adverse Event” and “Pregnancy” reported as AE leading to discontinuation.
 - Any “Other” reason classified as non-related to study treatment

All other missing MRI results will be handled as MNAR.

The following procedure for the different types of missing data will be performed:

- CUA lesion counts missing at the Baseline Period will be imputed from the distribution of available CUA lesion counts at the Baseline Period.
- CUA lesion counts missing at any post-Baseline Period that are considered MAR will be imputed from the distribution of available CUA lesion counts of the same post-Baseline Period.
- CUA lesion counts missing at any post-Baseline Period that are considered MNAR will be imputed from the distribution of CUA lesion counts of the Baseline Period

The changes from the Baseline Period will be calculated for all Periods and subjects, and the primary analysis (i.e. the Wilcoxon test as well as the mixed-effects linear model) will be repeated for each of the imputation repetition (i.e. for each of the imputed datasets).

Results combined using Rubin’s rule [5] will be presented.

Non-parametric factorial model

The primary analysis will be repeated using a factorial model for longitudinal data according to Brunner, Domhoff and Langer [2] (2002). Following the authors' terminology, a Fx-LD-F1 model will be assumed with x=2 fixed factors (age, EDSS at Baseline) and one longitudinal factor ('LD') which is reflecting Baseline and one of the primary post-Baseline Periods.

The underlying nonparametric hypothesis is defined in terms of the distribution functions. In a simple model with two time points and no fixed factors one would assume that the pairs of lesion count data (Baseline, post Baseline) would have marginal distributions F_s , $s=1, 2$, and the null hypothesis would be $H_0: F_1 = F_2$, the alternative accordingly $H_0: F_1 \neq F_2$. In a simple shift model one would assume that these marginal distribution functions only differ through a 'location parameter' μ , namely one would assume that $F_2(x) = F_1(x-\mu)$ and the null hypothesis would be $\mu=0$. For multiple fixed factors and one 'LD' factor the notation of hypotheses is more complicated and can be found in Brunner, Domhoff and Langer [2] (2002) in section 8.3 and especially in 8.3.1 for the null hypothesis of 'no time effect'.

Midranks over all CUA lesions from the Baseline Period and respective post-Baseline Period will be calculated. The ranks will be analyzed with a heteroscedastic factorial designs model with repeated measures (Baseline and one post-Baseline Period) and unspecified covariance matrices. The following factors will be used:

- Age groups ($\leq 40, >40$),
- EDSS at Baseline ($\leq 3 / >3$).

The p-value for the time effect will be calculated as described by Brunner, Domhoff and Langer [2] (2002).

Generalized linear model assuming negative binomial distribution

The standardized CUA lesion count will be evaluated using a generalized mixed-effects linear model with log link function. Period (i.e Baseline Period, each post-Baseline Period $i, i=1,2,3$) will be analyzed as a repeated factor accounting for within subject and within-center/region correlation using an unstructured covariance matrix. Age and EDSS at Baseline ($\leq 3, >3$) will be used as fixed effect covariates.

The ratio of the standardized CUA lesion count of each post-Baseline Period versus the Baseline Period will be calculated as the inverse log of the difference of the estimated contrast between each post-Baseline Period and the Baseline Period.

The CUA lesions are already standardized for the observation time and therefore no offset will be used. The estimated standardized CUA lesion count will be calculated based on the observed margin of the FAS at Baseline.

The estimates, standard deviation and 95% confidence intervals for the standardized CUA lesion count at each Period and the ratio between Periods will be presented together with the estimated fixed effects.

If the model doesn't converge a variance components covariance structure will be used instead of the unstructured covariance matrix.

14.2 Secondary Endpoints: Characterization of immune cell subsets count at the end of 3, 6, 12, 15, 18 and 24 months compared to Baseline

List of biomarker parameters per each panel is presented in Appendix 3. (Further, detailed information can be found in the corresponding DTA [9] and Parameter Mapping specification [10]).

Analysis (Analysis Set)	Derivation	Statistical Analysis Methods	Missing data handling
Secondary endpoint: Change of immune cell subset counts from Baseline to Month 3, 6, 12, 15, 18 and 24 Visits			
Secondary (FAS)	Change from Baseline in each immune cell subset count at Month i Visit, where i= 3, 6, 12, 15, 18 and 24.	
 • Descriptive summary statistics including percentage change. • Number of subjects with a value below LLOQ together with the LLOQ limit, if available. • Number of subjects with a value outside reference range (i.e. below lower limit or above upper limit of normal) with the reference range, if available. • 95% confidence intervals of the mean • Wilcoxon signed-rank test with the associate p-value • Box/scatter/time series plots. 	If cell count is missing for a Visit but the re-test is available, the value from the re-test will be used. Otherwise, the post-Baseline re-test results will be ignored for all analyses by Visit.

Handling of values below Lower Limit of Quantification (LLOQ):

Immune cell subsets reported as below the LLOQ will be imputed as follows:

- If the LLOQ is available then half of the LLOQ will be imputed,
- Otherwise, a zero will be imputed.

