The last non-missing measurement prior to start of study medication will serve as the Baseline measurement. Measurements performed on the day of first intake of study medication are assumed to be “prior to start of study medication”, as long as it has not been confirmed that the procedure was performed afterwards. This assumption is justified as following the sequence of procedures as specified in the study protocol. The intake of study medication should be the last procedure on the Visit day.

The MRI scans will be reconciled during central MRI review process. Therefore, MRIs will be considered as Baseline MRIs if assigned to the Baseline Visit by the central imaging review.

Definition of Study Periods

- Baseline Period: The Baseline Period is defined as the Period between the Screening and the Baseline MRI scan.
- Post-Baseline Period: The post-Baseline Periods that are used in the primary analysis are defined as follows:
 - Period 1 (p₁) is defined as the Period between Month 1 and Month 6 MRI scans.
 - Period 2 (p₂) is defined as the Period between Month 2 and Month 6 MRI scans
 - Period 3 (p₃) is defined as the Period between Month 3 and Month 6 MRI scans

In addition, the following post-Baseline Periods are defined solely for tertiary analyses:

Three months Periods

- Period 3.1 (p_{3.1}) is defined as the Period between Baseline and Month 3 MRI scans.

Six months Periods

- Period 6.1 (p_{6.1}) is defined as the Period between Baseline and Month 6 MRI scans,
- Period 6.2 (p_{6.2}) is defined as the Period between Month 6 to Month 12 MRI scans,
- Period 6.3 (p_{6.3}) is defined as the Period between Month 12 to Month 18 MRI scans,
- Period 6.4 (p_{6.4}) is defined as the Period between Month 18 to Month 24 MRI scans.

Periods excluding the Period between the Baseline scan and the Month 1 MRI scan:

- Period 11.1 (p_{11.1}) is defined as the Period between Month 1 to Month 12 MRI scans,
- Period 11.2 (p_{11.2}) is defined as the Period between Month 1 to Month 24 MRI scans.

Yearly Periods:

- Period 12.1 (p_{12.1}) is defined as the Period between Baseline to Month 12 MRI scans,
- Period 12.2 (p_{12.2}) is defined as the Period between Month 12 to Month 24 MRI scans.

2 -Year Period:

- Period 24.1 (p_{24.1}) is defined as the Period between Baseline to Month 24 MRI scans.

Sequential Visit Periods

- Period 100.0 (p_{100.0}) is defined as the Period between Screening and Baseline (equivalent to Baseline Period) MRI scans

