Tertiary Endpoint: CUA lesion count > 0			
Tertiary (FAS)	Cross-tabulation for each post-Baseline Period: 
 • No: $\#\text{CUA}(p_{\text{post-Baseline}}) = 0$ • Yes: $\#\text{CUA}(p_{\text{post-Baseline}}) > 0$ vs Baseline Period: 
 • No: $\#\text{CUA}(p_0) = 0$ • Yes: $\#\text{CUA}(p_0) > 0$ 	McNemar Test.	Missing observations at Baseline: Subjects with a missing Baseline score will not be included in McNemar Test, however separate cross-tabulation table including missing/not-evaluable lesions counts will be presented and thus providing percentage related to all subjects. Missing post-Baseline observations: Same as above but adapted for missing post-Baseline observations (see "Missing observations at Baseline").
Tertiary (FAS by subgroup High-relapse activity)			
Tertiary (FAS by subgroup "Previous treatment with DMDs")			
ΔCUA = Difference in the annualized CUA lesion count between post-Baseline Periods and the Baseline Period $\#\text{CUA}$ = Annualized CUA lesion count during Periods			

Analysis (Analysis Set)	Derivation	Statistical Analysis Methods	Missing data handling
p ₀ = Baseline Period \$=Sequential Visit Periods			

Mixed-effects linear model for repeated measures

The change from Baseline in the annualized CUA lesion count by Period or Visit (i.e. the Sequential Visit Period) will be analyzed by a repeated mixed-effects linear model, which adjusts for the Baseline score (i.e. the annualized count), age (in years), EDSS at Baseline (≤ 3 , > 3), pooled center, Period /or Visit, within subject correlation and time between scans (in years), where applicable. An unstructured covariance matrix will be assumed for the model. If the model doesn't converge an alternative covariance structure will be used instead.

The estimated annualized CUA lesion count will be calculated based on the observed margin of the corresponding analysis set at Baseline.

Mixed-effects linear model

The change from Baseline in annualized CUA lesion count for each Period separately will be analyzed by a mixed-effects linear model, which adjusts for the Baseline score (i.e., the annualized count), age (in years), EDSS at Baseline (≤ 3 , > 3), pooled center, time between scans (in years) and within subject correlation. An unstructured covariance matrix will be assumed for the model. If the model doesn't converge an alternative covariance structure will be used instead.

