14.3.3 T1 Gd+ lesion count

T1 GD+ lesion counts by Visit and Period are defined in Section 9 “Definition of Study Periods” and “Data Handling of MRI data”.

To evaluate further the course of T1 GD+ lesion appearance over time, T1 Gd+ lesions will be further classified as follows for each Visit:

- T1 Gd+ lesion count > 0
 - Yes (T1 Gd+ lesion count > 0)
 - No (T1 Gd+ lesion count = 0)

Analogously for new T1 Gd+ lesion count.

Analysis (Analysis Set)	Derivation	Statistical Analysis Methods	Missing data handling
Tertiary endpoints: Change from the Baseline Period in T1 Gd+ lesion count to the six months post-Baseline Periods			
Tertiary (FAS)	Period 6.1 (Baseline-Month 6): $\Delta T1(p_{6.1})$	Mixed-effects linear model for repeated measures, same as in Tertiary Analysis for Change from Baseline in CUA lesion count (see Section 14.3.1)	Same as in Tertiary Analysis for Change from Baseline in CUA lesion count (see Section 14.3.1)
Tertiary (FAS by subgroup "High-relapse activity")	Period 6.2 (Month 6-12): $\Delta T1(p_{6.2})$		
Tertiary (FAS by subgroup "Previous treatment with DMDs")	Period 6.3 (Month 12-18): $\Delta T1(p_{6.3})$ Period 6.4 (Month 18-24): $\Delta T1(p_{6.4})$		
Tertiary endpoints: Ratio of the six months post-Baseline Periods versus the Baseline Period in T1 Gd+ lesion count			
Tertiary (FAS)	Period 6.1 (Baseline-Month 6): $\#T1(p_{6.1})/\#T1(p_0)$	Generalized model assuming a negative binomial, same as in Tertiary Analysis for Change from Baseline in CUA lesion count (see Section 14.3.1)	Same as in Tertiary Analysis for Change from Baseline in CUA lesion count (see Section 14.3.1)
Tertiary (FAS by subgroup "High-relapse activity")	Period 6.2 (Month 6-12): $\#T1(p_{6.2})/\#T1(p_0)$		
Tertiary (FAS by subgroup "Previous treatment with DMDs")	Period 6.3 (Month 12-18): $\#T1(p_{6.3})/\#T1(p_0)$ Period 6.4 (Month 18-24): $\#T1(p_{6.4})/\#T1(p_0)$		
Tertiary endpoints: Change from the Baseline Period in T1 Gd+ lesion count to the yearly post-Baseline Periods			
Tertiary (FAS)	Period 12.1 (Baseline-Month 12): $\Delta T1(p_{12.1})$	Mixed-effects linear model for repeated measures as specified above.	Same as above for the mixed effect linear model with repeated measures.
Tertiary (FAS by subgroup "High-relapse activity")	Period 12.2 (Month 12-24): $\Delta T1(p_{12.2})$		
Tertiary (FAS by subgroup "Previous treatment with DMDs")			
Tertiary endpoints: Ratio of the yearly post-Baseline Periods versus the Baseline Period in T1 Gd+ lesion count			

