Tertiary endpoints: Ratio of the 2-year post-Baseline Period versus the Baseline Period in Annualized Active T2 lesions count			
Tertiary (FAS)	Period 24.1 (Baseline-Month 24): #T2(p _{24.1})/#T2(p ₀)	Generalized model assuming a negative binomial, same as in Tertiary Analysis for Change from Baseline in CUA lesion count (see Section 14.3.1)	Same as above for the generalized model.
Tertiary (FAS by subgroup "High-relapse activity")			
Tertiary (FAS by subgroup "Previous treatment with DMDs")			

Analysis (Analysis Set)	Derivation	Statistical Analysis Methods	Missing data handling
Tertiary endpoint: Change from Baseline in Annualized active T2 Lesion count by Visit			
Tertiary (FAS)	Change from Baseline in active T2 Lesion count at Month i Visit, where i=1, 2, 3, 6, 12, 15, 18 and 24.	Mixed-effects linear model for repeated measures, same as in Tertiary Analysis for Change from Baseline in CUA lesion count (see Section 14.3.1)	Same as in Tertiary Analysis for Change from Baseline in CUA lesion count (see Section 14.3.1)
Tertiary (FAS by subgroup "High-relapse activity")			
Tertiary (FAS by subgroup "Previous treatment with DMDs")			
Tertiary endpoint: Active T2 Lesion count > 0			
Tertiary (FAS)	Cross-tabulation for each post-Baseline Visit 
 No: #T2(p_{post-Baseline})= 0 Yes: #T2(p_{post-Baseline})> 0 vs Baseline Period: 
 No: #T2(p₀) = 0 Yes: #T2(p₀)>0 	McNemar Test.	Same as for McNemar test in Section 14.3.1
Tertiary (FAS by subgroup "High-relapse activity")			
Tertiary (FAS by subgroup "Previous treatment with DMDs")			
Tertiary endpoint: Change from Baseline in Total T2 Lesion count by Visit			
Tertiary (FAS)	Change from Baseline in Total T2 Lesion count at Month i Visit, where i=1, 2, 3, 6, 12, 15, 18 and 24.	Descriptive summary statistics.	
Tertiary (FAS by subgroup "High-relapse activity")			
Tertiary (FAS by subgroup "Previous treatment with DMDs")			
$\Delta T2(p_i)$ = Difference in the standardized/annualized total active T2 lesion count between Period i and the Baseline Period Further Periods or comparisons may be added by an Amendment to the IAP (a) 6-month interim analysis			

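### The McNemar tests on presence of lesions compare observation windows of unequal length or scan number, so most of them can be significant with unchanged disease activity

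*SAP*

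**What the plan says.** SAP 14.1.2 classifies each subject by whether the CUA count is zero or above zero and applies McNemar's test to Periods 1, 2 and 3 against the Baseline Period; the table row is headed "Presence of MRI activity (at least one CUA lesion) during the first 6 months (i.e., during Periods 1-3 compared to Baseline Period". Its stated aim is "To evaluate further the impact of the potential zero inflation". A three-level version of the standardized count gets Bowker's "test of symmetry".

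The final analysis repeats the zero / above-zero test:
- CUA (SAP 14.3.1): "Cross-tabulation for each post-Baseline Period", with McNemar's test against the Baseline Period.
- T1 Gd+ (SAP 14.3.3): the text says "T1 Gd+ lesions will be further classified as follows for each Visit", but the table compares each post-Baseline Period with the Baseline Period.
- Active T2 (SAP 14.3.7): "Cross-tabulation for each post-Baseline Visit", again against the Baseline Period.

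SAP Section 9 fixes the windows: "The Baseline Period is defined as the Period between the Screening and the Baseline MRI scan". Post-baseline windows run from one month to 24 months; Period 6.2, for example, "is defined as the Period between Month 6 to Month 12 MRI scans". The only correction for length and number of scans is standardization of the count (SAP 9 and 14.1.1). Protocol 8.5.1 makes all non-primary analyses exploratory but calls p of 0.05 or less nominally significant.

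**The concern.** A longer window, or one with more scans, gives a subject more chances to show at least one lesion. Dividing by time or by scans rescales a positive count but leaves zero at zero, so the flag discards the length and scan-number adjustment that Protocol 8.5.2 promises for the primary endpoint. McNemar's test asks whether two proportions are equal. With unequal windows they differ even if nothing has changed in the patient.

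The trial asks when the drug starts to act. An inert drug could appear to work within the first months on active T2, and an effective drug could appear to do harm in the long CUA windows. Readers will see these p-values beside the primary result.

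**Working it through.** The documents give no error rate or proportion for these tests, so there is no figure to reproduce.

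**Inputs from the documents**
- Baseline window: at least 4 weeks (28 days; Protocol 5.2) and at most 3 months + 7 days (97 days with the 30-day visit month of SAP 9; Protocol 7).
- Scans (SAP 9): Baseline 2, Period 1 four, Period 2 three, Period 3 two. Tertiary windows that start at Baseline leave out the Baseline scan, so Baseline-Month 12 has five scans and Baseline-Month 24 has eight.
- N = 265 (Protocol synopsis); two-sided 5%.

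**Assumed, not in the documents:** lesion rates, between-subject spread, duration of enhancement and the distribution of baseline gaps.

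**Step 1: break-even rate ratio.** With a constant lesion rate, the chance of at least one lesion depends on exposure. CUA exposure is the window length plus the enhancement time h seen on the first included scan; active T2 exposure is the window length. Break-even ratio = baseline exposure / window exposure. Below 1, unchanged activity looks like worsening; above 1, like benefit. With h of 15 to 30 days and gaps of 28 to 97 days:

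| Window | Lowest | Highest |
|---|---|---|
| CUA Period 1 (150 days) | 43/165 = 0.26 | 127/180 = 0.71 |
| CUA Period 2 (120) | 43/135 = 0.32 | 127/150 = 0.85 |
| CUA Period 3 (90) | 43/105 = 0.41 | 112/105 = 1.07 |
| CUA Baseline-Month 12 (360, first scan excluded) | 43/360 = 0.12 | 127/360 = 0.35 |
| CUA Baseline-Month 24 (720, first scan excluded) | 43/720 = 0.06 | 127/720 = 0.18 |
| CUA Period 100.1 (30, first scan excluded) | 43/30 = 1.43 | 127/30 = 4.23 |
| CUA Periods 100.2, 100.3 (30) | 43/45 = 0.96 | 112/45 = 2.49 |
| Active T2, Months 1-3 (30) | 28/30 = 0.93 | 97/30 = 3.23 |
| Active T2, Months 6, 15, 18 (90) | 28/90 = 0.31 | 97/90 = 1.08 |
| Active T2, Months 12, 24 (180) | 28/180 = 0.16 | 97/180 = 0.54 |

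**Step 2: worked example.** Take 0.3 lesions per month, gamma shape 0.5, one-month enhancement and a 2-month baseline gap. P(no lesion) = (1 + 0.3e/0.5)^-0.5, with e the exposure in months.
- Baseline, e = 3: 2.8^-0.5 = 0.5976, so 40% are above zero.
- Period 1, e = 6: 4.6^-0.5 = 0.4663, so 53% are above zero.
- Zero in both, e = 9: 6.4^-0.5 = 0.3953.
- Zero at baseline only: 0.5976 - 0.3953 = 0.2023, about 54 of 265. Zero in Period 1 only: 0.4663 - 0.3953 = 0.0710, about 19 of 265.
- Chance of p < 0.05 with no change in activity: 98.6%. Period 2 (50% above zero) gives 87%, Period 3 (46%) gives 42%.
- Control: with a 3-month baseline gap against Period 3 the exposures match, the discordant cells are equal, and rejection is 5.0%. Unequal windows are therefore the cause.

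**Step 3: simulation with no effect.** Rates 0.25 to 1.0 per month, gamma shape 0.5 to 1, exact McNemar. Share of trials significant in the direction shown:

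| Test | Gaps uniform 28-97 days | All 97 | All 28 |
|---|---|---|---|
| CUA Period 1, worsening | 95-100% | 40-76% | 100% |
| CUA Period 2, worsening | 76-98% | 10-24% | 100% |
| CUA Period 3, worsening | 30-66% | 0-1% | 98-100% |
| CUA Baseline-Month 12, worsening | 100% | 100% | 100% |
| Active T2 Months 1-3, benefit | 90-100% | 100% | 0-1% |
| Active T2 Months 12 and 24, worsening | 100% | 91-99% | 100% |

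CUA in Period 100.1 gives false benefit in 39-100%.

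**Step 4: T1 Gd+.** Only the number of scans matters if enhancement is shorter than the gaps. Three scans against two give false worsening in 42-87%, four in 91-100%, five or eight in 100%. Two against two give 1-5% with fixed enhancement up to one month, but 14-65% if enhancement is exponential (mean 1 to 2 months) and all gaps are 28 days. One visit scan against the two baseline scans would give false benefit in 73-100% with fixed enhancement.

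**Step 5: Bowker.** It rejects in 89-100% / 35-83% / 100% for Period 1 and 30-56% / 5-7% / 100% for Period 3 (same three gap patterns), without a fixed direction. With 91-day gaps, Period 1 against baseline, the share at zero falls from 33.1% to 25.6% (worse) while the share above 1 falls from 28.5% to 24.2% (better).

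**The case against.** The strongest reply is that little depends on these tests. They are sensitivity or tertiary analyses with no decision rule, the categorization is there to explore zero inflation, and models on standardized counts stand beside it. That is right, and it limits the weight of the point. It does not make a p-value interpretable when its null is false by construction.

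Four stronger readings are tempting but unsupported:
- *Every one of these nulls is false.* Period 3 has two scans, like Baseline, and its roughly 3 months lie inside the allowed baseline gap. Two-scan T1 Gd+ windows stay near nominal unless enhancement outlasts the baseline gap.
- *T1 Gd+ by Visit will show a false benefit.* SAP 14.3.3 speaks of each Visit in its text and of Periods in its table. It does not clearly specify one visit scan against two baseline scans; the bias exists only if it is run that way.
- *The bias in Periods 1 and 2 is safely conservative.* That holds only for constant activity. Subjects are selected for recent relapses, so untreated decline is plausible and would push every result towards benefit. By Step 1, a fall in rate of 29-74% would cancel the Period 1 bias. With an assumed 30% fall, 91-97 day gaps and one-month enhancement, Period 1 rejects in about 4-5% overall, and Period 2 shows benefit in 11-22%.
- *The primary result is compromised.* The confirmatory test is the Wilcoxon signed-rank test on differences in standardized counts (SAP 14.1.1), not on the flag.

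**Conclusion.** The concern holds within limits. If disease activity is constant, the McNemar null is false as follows:
- CUA in Periods 1 and 2 and in windows of 5 months or longer: towards worsening at every allowed gap.
- CUA in Period 3, and active T2 at Months 6, 15 and 18: only where baseline gaps differ from about 3 months, towards worsening if shorter.
- Active T2 at Months 12 and 24: towards worsening.
- Active T2 at Months 1-3, and CUA in Periods 100.2 and 100.3: towards benefit when the gap is clearly over 1 month. CUA in Period 100.1: towards benefit at every gap, because the Baseline scan is excluded.
- T1 Gd+ in windows with more than two scans: towards worsening.

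Bowker's test is affected too, in no fixed direction. The directions follow from the schedule and constant activity; the error rates also rest on assumed lesion rates and gaps, whose distribution the documents do not give. This deserves correction because several p-values bear directly on onset of action, but it leaves the confirmatory test alone.

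**What to change.** 1. In SAP 14.3.3, reconcile the text and the table: for T1 Gd+ by Visit, test each visit scan against the single Baseline Visit scan. With no effect, this gave 1-3% significant per side in every setting simulated. Two-scan T1 Gd+ windows may keep McNemar's test, with a note that they lean towards worsening if many baseline gaps are near 4 weeks.
2. For CUA, active T2 and T1 Gd+ windows with other than two scans, drop the McNemar and Bowker p-values. Show the cross-tabulations descriptively, beside the window length and scan number already summarised under SAP 10.1. CUA in Period 3 may keep its test if limited to subjects whose baseline gap is close to 3 months.
3. SAP 6.1 places the sensitivity analyses at the 6-month analysis and 6.2 does not repeat them, so add a caveat to the report for the Period 1-3 tests.

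The cost is wording and fewer simple p-values; no new data are needed and the models on standardized counts remain. The scan-against-scan test covers enhancement only. Matching exposure does not remove natural decline, which a single arm cannot separate from drug effect.
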